### Sample Size and Power.

The current study is primarily concerned with deriving a preliminary range of plausible effect sizes for the effect of treatment; as such, power estimates are provided here purely as due diligence. Frequentist estimates rely on G\*Power 3.1.9.7 and focus on a simplified model predicting the effect of treatment on one given normally-distributed outcome. Assuming two-sided alpha = 0.05, N = 12, 3 total measurements, a correlation among repeated measures of  $r = 0.15$ , the current proposal has 80% power to detect an effect size Cohen's  $f = 0.59$ . Notably, Bayesian inference will provide probabilistic estimates of the effect of treatment irrespective of sample size.

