The primary goal of the study is to assess the effects of SUVO on physiological sleep (actigraphy, EEG) and self-reported sleep quality. We will also assess two other domains linked to the orexin system and commonly related to MA relapse including stress and cue reactivity/craving. Our overarching hypothesis is that treatment with SUVO will attenuate disruptions in sleep, stress, and cue reactivity/craving. By engaging these relapse-related target mechanisms, this work will provide critical proof-of-concept evidence for a subsequent R01. To that end, we will employ a within-subjects, two group cross-over design (N=12) and take a multimodal approach to assessing sleep, stress, and cue reactivity/craving. Participants will complete stress reactivity and electroencephalogram (EEG) laboratory tasks, self-report, and drug use measures after one week of SUVO, washout, and placebo (PL), order counterbalanced between groups. Participants will also wear an activity watch at night in order to have their sleep monitored via actigraphy.

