### Primary Hypotheses and Specific Aims:

Primary Aim 1: Determine the effects of SUVO on sleep, stress, and cue reactivity/craving

Hypothesis 1a: SUVO compared to placebo will improve sleep outcomes assessed by actigraphy (total sleep time, wake after sleep onset), self-report (Pittsburg Sleep Quality Index), and EEG (resting state alpha power);

Hypothesis 1b: SUVO compared to placebo will improve acute stress reactivity as measured by physiological responses (cold-pressor task induced cortisol and HR/BP) and subjective ratings (Visual Analog Scale; Depression Anxiety Stress Scale).

Hypothesis 1c: SUVO compared to placebo will reduce cue reactivity/craving as measured by LPP to methamphetamine images and self-report (Brief Substance Craving Scale).

Exploratory Aim 2: Evaluate the preliminary safety and side effects profile of SUVO.

**Primary outcome measures:** self-reported sleep, resting state alpha power, LPP, self-reported stress, and cortisol measured at each study visit after 1-week of SUVO, washout, and PL; total sleep time and wake after sleep onset measured nightly via actigraphy watch

**Secondary outcome measures:** methamphetamine use (TLFB and UDS) measured at each study visit after 1-week of SUVO, washout, and PL; side effects questionnaire, BDI, and CSSRS measured at each study visit after 1-week of SUVO, washout, and PL

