## Methods:

**Overall study design.** We will use a two-group cross-over design. Each group will complete three conditions, each lasting one week. 12 participants will be randomized to one of the two groups. Group one (n=6) will receive one-week placebo, one-week washout, and one-week SUVO. Group two (n=6) will receive one-week SUVO, one-week washout, and one-week placebo. During the washout period, the participants will not receive any pills. Eligibility criteria and baseline measures will be collected on Day 0 before the start of week one. Participants will come to the clinic once a week on Monday for 4 weeks. On Day 1 (Monday) of the first week, the participants will receive their medication and actigraphy watches. Each following Monday, they will complete self-report and drug use measures, as well as the laboratory tasks (cold pressor and EEG). Table 1 outlines the schedule of assessments. We will aim to enroll a total of 16 participants to complete 12, with dropouts being replaced, if possible.

**Participants, Recruitment, and Setting.** The participants will consist of non-treatment-seeking individuals meeting DSM-5 criteria for MA use disorder. All participants will be between the ages of 18-45 and fluent in English. IRB NUMBER: HSC-MS-22-0796 IRB APPROVAL DATE: 10/09/2023

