### Specific Hypothesis Testing.

**Aim 1:** GLMM for repeated measures will separately model each outcome measure as a function of treatment condition, with Level-2 effects included for best fit. Outcomes will include measures of sleep (H1a: actigraphy; self-report sleep quality; EEG), acute stress reactivity (H1b: physiological responses; subjective ratings) and cue reactivity/craving (H1c: LPP to methamphetamine images; self-report craving)

**Aim 2:** Descriptive statistics will evaluate the frequency of adverse events (AEs) and severe adverse events (SAEs) between and within conditions. Logistic regression will evaluate presence (vs. absence) of specific AEs as a function of condition.

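### The stated 80% power at f = 0.59 is not what the plan's inputs give for a within-person treatment effect (f = 0.51 to 0.52 under sphericity), and the test behind it is not named

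*Combined protocol and SAP*

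**What the plan says.** The Sample Size and Power section says its frequentist estimates come from G*Power 3.1.9.7 and "focus on a simplified model predicting the effect of treatment on one given normally-distributed outcome". The inputs are given as "Assuming two-sided alpha = 0.05, N = 12, 3 total measurements, a correlation among repeated measures of" 0.15. The result is that "the current proposal has 80% power to detect an effect size Cohen's" f = 0.59. No test, number of groups or epsilon is stated. The section also says that "power estimates are provided here purely as due diligence".

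The rest of the plan makes treatment a within-person factor. Under Methods, Overall study design, there are two groups of six, one taking placebo, washout and suvorexant and the other the reverse order: "Each group will complete three conditions, each lasting one week". Under Specific Hypothesis Testing, Aim 1, "GLMM for repeated measures will separately model each outcome measure as a function of treatment condition". The Aim 1 hypotheses all set suvorexant against placebo; Hypothesis 1a, for example, begins "SUVO compared to placebo will improve sleep outcomes assessed by actigraphy".

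**The concern.** The three measurements in the power statement correspond to the three one-week conditions that each participant completes, so the natural reading is a repeated-measures test of condition within person. Under sphericity that test does not give f = 0.59 with the stated inputs. The option that does give it, with nothing changed or added, is a between-groups test. Both groups receive suvorexant and placebo, so a comparison of group averages over all visits carries no information on suvorexant versus placebo.

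This is the plan's only power figure, and a reader cannot tell which test or contrast it covers. The choice of test also decides how the figure responds to its assumptions. As the correlation among repeated measures goes from 0 to 0.3, the detectable f falls from 0.555 to 0.464 for the within-person test (one group) and rises from 0.518 to 0.656 for the between-groups test. The study is meant to support a later grant application, so the detectable effect should be traceable to the comparison of interest.

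**Working it through.** **Inputs** (Sample Size and Power): two-sided alpha 0.05, N = 12, m = 3 measurements, r = 0.15, power 80%, f = 0.59. The number of groups k is not stated there; the design has 2 sequence groups, and k = 1 is tried as well. Epsilon is not stated and is assumed to be 1 unless noted. All power values use the noncentral F distribution with noncentrality λ.

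**1. Reproducing 0.59: between-factors test, k = 2**

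- λ = f²·N·m / [1 + (m − 1)r] = 0.3481 × 36 / 1.30 = 9.64
- df = k − 1 = 1 and N − k = 10; critical F = 4.965
- Power at f = 0.59 is 79.9%; 80% power is reached at f = 0.591.

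The stated figure is recovered without changing or adding any input.

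**2. Within-person test, same inputs, epsilon = 1**

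- λ = f²·N·m·ε / (1 − r) = 0.3481 × 36 / 0.85 = 14.74 at f = 0.59
- df = (m − 1)ε = 2 and (N − k)(m − 1)ε = 22 for k = 1, or 20 for k = 2; critical F = 3.443 or 3.493
- 80% power needs λ = 11.08 (k = 1) or 11.24 (k = 2). Solving for f:
  - k = 1: √(11.08 × 0.85 / 36) = 0.511
  - k = 2: √(11.24 × 0.85 / 36) = 0.515

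The group-by-condition interaction with k = 2 has the same λ and degrees of freedom, so it also gives 0.515.

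**3. Other routes to about 0.59**

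- *Within-person test with epsilon below 1.* Exactly 0.59 needs epsilon = 0.689 (k = 1) or 0.704 (k = 2). Values of f that round to 0.59 (0.585 to 0.595) correspond to epsilon from 0.704 down to 0.674 (k = 1), or from 0.719 down to 0.689 (k = 2).
- *Two conditions only, m = 2.* At f = 0.59, λ = 0.3481 × 24 / 0.85 = 9.83. The f for 80% power is 0.579 (k = 1) or 0.585 (k = 2). This does not use the stated three measurements.

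| Test | f at 80% power | Power at f = 0.59 |
|---|---|---|
| Between groups, m = 3, k = 2 | 0.591 | 79.9% |
| Within person, m = 3, ε = 1, k = 1 | 0.511 | 90.4% |
| Within person, m = 3, ε = 1, k = 2 | 0.515 | 89.9% |
| Within person, m = 2, k = 1 | 0.579 | 81.4% |
| Within person, m = 2, k = 2 | 0.585 | 80.6% |

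**4. The hypothesised contrast as a paired comparison**

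For a paired t test in 12 completers (11 df, two-sided 0.05), 80% power needs dz = 0.889. In units of the outcome SD, d = dz·√[2(1 − r)] = 0.889 × √1.70 = 1.159. For two conditions f = d/2, so this is f = 0.579, and the stated f = 0.59 would be d = 1.18.

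**5. Simulation check** (200,000 trials per case, equal pairwise correlations of 0.15)

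- Within-person F test, k = 1: power 0.802 at f = 0.511 and 0.903 at f = 0.59
- Between sequence groups: 0.799 at f = 0.59
- Paired t: 0.814 at d = 1.18 and 0.801 at d = 1.16

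**The case against.** The best defence is that 0.59 may be a correct figure that is poorly documented. An epsilon near 0.70 gives it for a within-person test with every stated input intact, and the planned mixed model does not commit to sphericity. For the contrast the hypotheses concern, suvorexant against placebo, power at f = 0.59 is 80.6% to 81.4%, within about 1.5 points of the stated 80%. The three-condition test includes the no-pill washout week, which is not itself a hypothesis, so quoting 0.51 to 0.52 would make the study look more sensitive without describing the comparison of interest. On this view the fault is only that the test is not named.

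Much of this stands. The between-groups source is an inference, the practical effect is small, and under sphericity the error is on the cautious side. It does not rescue the sentence as written. A single common correlation among the repeated measures, taken with equal variances, is compound symmetry, for which epsilon is 1; a value near 0.70 would be a further assumption that should have been stated. The two-condition route drops the stated three measurements. Of the routes examined, only the between-groups test gives 0.59 from exactly the stated inputs, and it is not a test of treatment in this design.

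**Conclusion.** The concern holds, as a minor one. For a within-person treatment effect with the stated inputs and epsilon = 1, 80% power corresponds to f = 0.511 to 0.515, not 0.59, and power at 0.59 is about 90%, not 80%. The size of the mismatch rests on sphericity, which the plan neither states nor rules out. That the test is unnamed rests on no assumption. A two-group between-factors calculation is the likeliest source, but the document cannot settle it. The figure determines neither the sample size nor any decision rule, and for a two-condition suvorexant–placebo contrast it happens to be nearly right.

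**What to change.** In Sample Size and Power, replace the figure with one for the within-person test and name the procedure. Either of these sentences would do:

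1. *For the SUVO-minus-placebo contrast, paired comparison in 12 completers (11 df, two-sided 0.05), there is 80% power for dz = 0.89, i.e. d = 1.16 at r = 0.15.*
2. *For the three-condition within-person F test (N = 12, 3 measurements, r = 0.15, epsilon = 1) there is 80% power for f = 0.51 to 0.52.* If another epsilon was used, state it and the f that goes with it.

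The first is the better choice because it describes the contrast in the Aim 1 hypotheses. The cost is one sentence in the protocol, with no change to design, analysis or sample size.

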### Protection of Human Subjects:

#### Recruitment and Informed Consent

The study will be conducted at the Center for Neurobehavioral Research on Addiction (CNRA), where the PI ([name]) and Co-Is (Drs. [name], [name], [name], [name]) have experience conducting treatment and laboratory-based studies in substance use populations. Recruitment will follow typical CNRA protocols, including local advertising in print/radio, recruitment companies (Build Clinical/TrialFacts) and referrals from prior CNRA studies and the Houston area. We will also recruit from the Department of Psychiatry Recruitment Registry: HSC-MS-23-0768. Our study and contact information will be shared with potential subjects that are on the psychiatry waitlist via the Department of Psychiatry website or e-mail blasts. Individuals who call for information will be given a brief description of the study. Those interested will then be asked to answer questions about their current substance use. A trained research assistant will conduct this telephone-screening interview. Eligible subjects will be scheduled for an in-person intake visit at the CNRA, first floor BBSB. The first intake appointment will begin with the presentation of the informed consent form. The consent form will detail the requirements of study participation (e.g., # of visits, type of data collected, time commitment, etc.).

Subjects will be told that the purpose of the study is to evaluate the effects of medications on human behavior related to mood, sleep, and methamphetamine cravings/use. Information about the components of the experimental procedure will be explained. Details of the random assignment procedure (placebo or active dose) will be explained. Subjects will be informed of their attendance expectations. Other information on the consent form will include a full description of study requirements, reimbursement, risks, benefits, alternatives, and the role of the local IRB. All questions will be answered before written consent is requested. All research conducted in our laboratory and the CNRA has prior approval from the Committee for the Protection of Human Subjects (CPHS) of the University of Texas Health Science Center - Houston.

### Selection Criteria

Eligible participants will:

1. Be between the ages of 18 and 65 years old
2. Meet DSM-5 criteria for methamphetamine use disorder
3. Be fluent in English and able to understand the consent form

Participants will be excluded if they:

1. Have an alcohol use disorder or report binge drinking (>7 drinks for women and >14 drinks for men)
2. Have a greater than mild substance use disorder on any other illicit substance
3. Have any medical conditions contraindicating SUVO (e.g., severe pulmonary disease, severe cardiovascular disease or clinically abnormal ECG, severe liver or kidney disease, seizure disorder, or sleep disorder – particularly narcolepsy)
4. Are currently taking medications with known drug interactions with SUVO (e.g., MAO inhibitors, anticonvulsants, haloperidol, phenothiazines, anesthetics, and any sedative)
5. Are pregnant or breast feeding
6. BMI > 30 (women only)
7. Have a current DSM-5 psychiatric disorder or neurological disease requiring on-going treatment that would make participation unsafe
8. Have history of seizure disorder

9. Have a head injury with loss of consciousness in the last 5 years

Assessment of Criteria

Eligibility will be carefully assessed in person at the CNRA. Participants will receive a full physical and psychiatric evaluation on the first day including: a medical-history questionnaire, physical examination, urine drug screen, pregnancy test, and ECG. SCID-5 will be conducted by licensed counselors and the physical examination will be performed by medical director ([name], M.D.).

Sources of Materials

We will obtain information about subjects from structured interview evaluations, physical examinations, self-report measures, and computerized behavioral tasks. This information will be collected at specified time points during the study phases of eligibility/baseline assessment, experimental testing, and end-of-study. The biological specimens obtained from all subjects will include urine, saliva for cortisol assessment, and breath samples for alcohol detection. Individuals who volunteer to participate will be assigned a subject number (e.g., 15000), under which all information collected will be filed. All materials will be obtained for the specific purposes of this research.

Potential Risks

**Study Medication (suvorexant).** Suvorexant (BELSOMRA®) is an orexin receptor antagonist indicated for the treatment of insomnia, characterized by difficulties with sleep onset and sleep maintenance. Recommended dose is 10 mg, 1x per night taken within 30 minutes of going to bed, with at least 7 hours of planned time before awakening. If the 10 mg dose is well tolerated but not optimally effective, it can be increased but not to exceed 20 mg once daily. Medication is taken PO, with dosage in tablets of 5, 10, 15, and 20 mg. Contraindicated in patients with narcolepsy. Precautions include daytime somnolence; dose-related risk of impaired alertness and motor coordination, including impaired driving; patients taking 20 mg should be cautioned against next-day driving; nighttime “sleep-driving” and other complex behaviors while out of bed and/or not fully awake; worsening of depression or suicidal thinking; compromised respiratory function; sleep paralysis, hypnagogic/hypnopompic hallucinations. Risk of the above symptoms increases with use of CNS depressants and alcohol. In obese women (BMI > 30), there is increased risk of exposure-related adverse effects. Belsomra® is a schedule-IV compound with mild/modest abuse-potential in the same class as existing sleep medications and anxiolytics. The most common adverse reactions include somnolence and slowed motor coordination. Not recommended for use in patients taking strong CYP3A inhibitors, efficacy may be reduced, or for patients with severe hepatic impairment. Based on animal data, Belsomra® may cause fetal harm.

**Psychometric Testing.** Items on certain psychological/psychiatric questionnaires and interviews might be perceived as personally discomforting to some subjects.

**Actigraphy.** Participants may experience mild discomfort while acclimating to wearing the device during sleep.

**EEG Task.** The EEG may lead to redness or skin irritation where the sensors are placed. This will almost always disappear after a few hours. The images that the participants will view will contain sexual and violent images (including erotic scenes and mutilated bodies) and may upset some participants. Viewing drug images can induce craving.

**Cold Pressor Task.** Individuals with cardiovascular disorders and neurological disorders should not participate. This information will be obtained during medical screening. Due to individual variation in pain and cold sensitivity, for some subjects the cold water may become too painful to sustain immersion for 90 seconds. There are no lasting effects (physical or physiological) from placing the hand and wrist in ice water (0° Celsius) for 90 seconds.

**Psychiatric/Physical Examination.** There is a slight risk of bruising and infection in the blood draw procedures. Disclosing mental health information during the clinical interview can be uncomfortable for some participants.

**Confidentiality.** There is always a risk of loss of confidentiality when participating in research.

Adequacy of Protection Against Risks

**Study Medication (suvorexant).** We will screen very carefully for alcohol use and suicide symptoms. It will be made explicit that participants should not drink alcohol for the duration of the study. We will use the mental health counselors SCID-screener to enroll only those with low risk for alcohol abuse. The Columbia Suicide Severity Rating Scale (CSSRS) will be administered at each visit (see additional details below), as per NIH/FDA guidelines. Indication of regular alcohol use by SCID, intake self-report, or breath alcohol, or indication of increase in suicidality as measured by the CSSRS will result in study stopping (see details below). Will exclude for any patients taking CYP3A inhibitors, patients with severe hepatic impairment; and women who are or become pregnant. Pr  IRB NUMBER: HSC-MS-22-0796  
drugs tests are administered  
IRB APPROVAL DATE: 10/09/2023

on via urinalysis on lab testing days. Women of childbearing capacity must be taking one form of birth control. We will exclude for women with BMI > 30 to decrease risk of side effects.

In addition to the rigorous screening criteria for inclusion. At the end of each experimental day, cardiovascular measures will be taken and the subject will be evaluated for signs of impairment or side effects, by a research assistant and then by the research nurse, medical director, or PI. The assessment battery includes subjective effects questionnaire, nystagmus, touching nose, balance, and walking a straight line). If cardiovascular measures are normal, within the range of pre-dose levels, and the subject is determined to be unimpaired, the subject will be released. If any signs of intoxication are detected, participants will be required to remain at the experimental site until such symptoms are no longer observed.

In the event of either an unexpected adverse event or a prolonged period of intoxication, we have several measures in place. First, [name] (CNRA medical director) has clinical experience and training in emergency medicine. Thus, a physician will be in the immediate vicinity of laboratory at all times. Offices and clinical space are within 100 feet of the lab. Collaborating MDs can be paged at any time during the day. Second, Ben Taub Hospital, a level 5 emergency medical center is located just minutes away from BBSB. Finally, in the event of extended sedation, intoxication, or impairment, in which any subject does not appear clear-headed, feeling well, and in full control of his or her behavior, two steps will be taken. First, the subject will remain in the lab until such time that the primary or a co-investigator deems that it is safe for him or her to leave (e.g., passing the sobriety test described above). In the event of extended impairment, we will arrange (and pay for) a taxi service to drive the subject back to his/her home rather than having to use METRO. We will administer the Columbia Suicide Severity Rating Scale (CSSRS screening version) at each visit to assess suicidality and depressive symptoms, consistent with current FDA best practices. If the screening indicates change in suicidal ideation, we will administer the full version. If suicidality is judged to clinically significant as per CSSRS scoring criteria, we will (1) report the event to CPHS within 48 hours; (2) remove the patient from the study; (3) make a referral to either the BBSB outpatient mood disorders clinic or UT HCPC, depending on consultation from Dept of Psychiatry outpatient faculty at BBSB.

The following procedures will be taken to safeguard against adverse medication events: (1) careful initial intake evaluation to determine eligibility based on inclusion/exclusion criteria; (2) thorough physical evaluation prior to treatment, consisting of physical examination, standard laboratory tests, electrocardiogram, toxicology screen, pregnancy test, and vital signs; (3) repeated tests during treatment; (4) daily monitoring of pill taking via CAROMA, returned pill counts, and self-report; (5) weekly review of adverse events and medication compliance; (6) regular evaluation by the study physician ([name]). Specific criteria will be used to exclude potential subjects for whom any of the study medications is contraindicated. Any abnormal physiological, psychological, or behavioral event will be evaluated and, if indicated, will result in the subject's removal from the study.

We will use an Adverse Event Log (AEL) based on NIDA SAFTEE procedures. The AEL will record the duration, severity, and frequency of any adverse events, signs, and symptoms. An evaluation will be made as to the event's relationship to the study drug(s), scaled as unrelated, unlikely, possible, and probable. The AEL will be included in the report to DSMB.

Subjects will be monitored regularly for compliance with the study requirements, including the dosing regimen and breath alcohol testing upon arrival at the laboratory each day of testing. Written and verbal information about the medication will be given to all participants. This information will remind the subject to: (1) take food shortly after medication if needed to relieve gastric irritation; (2) inform the treatment research clinic nurse or physician of any over-the-counter and prescription medication taken, especially: cough medication, diarrhea medication, narcotic medication; (2) notify treatment research clinic nurse or physician of any side effects that persist or worsen. The study physician, nurse, and PI will review cases involving clinical deterioration of increased symptomatology or substance abuse. Appropriate actions will be taken, including study termination with proper referral.

**Behavioral and Psychometric Testing.** The participants do not have to answer any questions they do not feel comfortable answering and can not take part in the study.

**EEG Task.** Participants will be shown example images during the consent process and will be told they can stop viewing the images at any time. Those who think they will be affected by the pictures (erotic, mutilations, and drug-related images) can choose to not participate.

**Cold Pressor Task.** Participants will be told that if the level of pain is too uncomfortable, they should remove the hand immediately. Each participant will be able to test the water temperature for 10 sec prior to beginning the procedure. These details are presented in the informed consent document.

**Psychiatric/Physical Examination.** Our experienced phlebotomist will take any precautions to

IRB NUMBER: HSC-MS-22-0796  
UTHealth Houston  
IRB APPROVAL DATE: 10/09/2023

prevent unnecessary bruising during venipuncture. All risks and protections are discussed further in the general evaluation of eligibility protocol (HSC-MS-0322).

**Confidentiality:** Confidentiality will be protected in several ways. All information collected solely for research purposes will be kept in locked, restricted access files. Individual subject information will be transferred to outside sources only with the express written request of the subject. Subjects will receive a copy of their signed consent form. All personnel associated with this grant have successfully completed ethics training in the Protection and Welfare of Human Participants, and certification is on file at the Health Science Center CPHS and office of sponsored projects. All intake and experimental data that are collected will be uploaded onto a laboratory database, computers dedicated to data storage and management. These computers are protected by password. All data will be treated as confidential information. All data including urine samples, medical and psychiatric intake exams, and behavioral and drug administration data – will be obtained solely for research purposes. All individuals who elect to participate and sign the informed consent agreement will be assigned a subject number (e.g., 15000), which will serve as that subject's identifier (rather than name or SS#). A log book and electronic database that connect participants' identifying information with subject number are kept in a locked file cabinet and room and password protected, respectively.

